#### **11.10.2. Vital signs**

The results of the vital signs measurements will be listed by subject and time-point including the date/time of the assessment, flags for measurements that are outside the reference range (L or H, if applicable), changes from baseline and repeat/unscheduled measurements. The baseline for vital signs measurements will be the pre-dose assessment on Day 1 in each treatment period. Descriptive statistics will be presented by treatment and time-point for both observed values and changes from baseline.

#### **11.10.3. Resting 12-lead electrocardiogram**

12-Lead ECG results will be listed for each subject.

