### **Safety data analysis**

The safety analysis set will include all subjects who received at least one dose of naloxegol and for whom any safety post-dose data are available.

Subject disposition will be listed and summarized including the number of withdrawals and the primary reason for withdrawal. Subjects excluded from any analysis sets will be listed including the reasons for exclusions.

All safety data will be listed for each subject and summarized appropriately. Adverse events will be coded using Medical Dictionary for Regulatory Activities (MedDRA) and summarized by preferred term (PT) and system organ class (SOC). Additional summaries by severity and causality will be presented.

All clinical safety laboratory data and vital signs measurements will be listed and summarized by treatment or treatment sequence (as applicable) including changes from baseline. Any out of range laboratory measurements will be flagged in the listings. Other safety data including C-SSRS, physical examinations and ECG will be listed for each subject.

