#### **5.4.1. Absorption and food-effect**

The investigational medicinal product (IMP) acts within the GI tract. Following oral administration, naloxegol is absorbed rapidly, with peak concentrations ( $C_{max}$ ) achieved in less than 2 hours. In a majority of subjects, a secondary plasma concentration peak of naloxegol was observed approximately 0.4 to 3 hours after the first peak. Enterohepatic recirculation may be an explanation as extensive biliary excretion was seen in the rat [4, 5].

A high-fat meal increased the extent and rate of naloxegol absorption. The  $C_{max}$  and area under the plasma concentration-time curve (AUC) were increased by approximately 30% and 45%, respectively [5].

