-  Ambulatory visits: Screening and Day 4 to each treatment period, and final follow-up/early termination (ET) visit\*\*.
-  IMP administration: On Day 1 at 0 hours to each treatment period.
-  Questioning will be conducted spontaneously plus at the following scheduled time-points to each treatment period: pre-dose (0 hours) and post-dose at 3, 12, 24 and 48 hours. Serious adverse events (SAEs) will be recorded from the signing of informed consent and adverse events (AEs) will be recorded from randomization until the final follow-up/ET visit. Data to be collected for statistical analysis are described in [Section 11.10.1](#).
-  Blood pressure (BP) and pulse measurements (supine position) will be collected at screening and for each treatment period on admission, at pre-dose (0 hours) and post-dose at 24 and 48 hours, as well as at the final follow-up/ET visit.
-  12-Lead electrocardiogram (ECG) will be performed at screening, first admission to the clinical unit (Visit 2, Day -1), 1.25 hours after each dose (Visits 2-5, Day 1), as well as at the final follow-up/ET visit (total of 7 ECGs per subject who complete the study).
-  Hematology, clinical chemistry and urinalysis will be performed at screening and at the final follow-up/ET visit; in addition, for the first and third treatment period at pre-dose.
-  Serum pregnancy test at screening; urine pregnancy tests thereafter (females only).
-  Full physical examination will be performed at screening and the final follow-up/ET visit. Abbreviated physical examination will be performed on admission and at 48-hours post-dose to each treatment period.
-  C-SSRS will be performed at screening (version Baseline - Screening) and at the final follow-up/ET visit (version Since Last Visit) (see [Appendix 15.5](#)).
-  Prior and concomitant medications are defined, and data to be collected for statistical analysis are described in [Section 11.8.1](#).
-  Blood samples for the determination of plasma concentrations of naloxegol will be collected for all treatment periods at the following time-points: pre-dose (0 hours [within 30 minutes prior to IMP administration]) and post-dose at 0.25 (15 minutes), 0.5 (30 minutes), 1, 1.5, 2, 3, 4, 5, 6, 8, 10, 12, 16, 24, 36, 48 and 72 hours (18 samples per treatment period).

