### **9.3.3. Resting 12-lead electrocardiogram**

A 12-lead ECG will be obtained after the subject rested in the supine position for at least 10 minutes. The investigator will judge the overall interpretation as normal or abnormal. If abnormal, it will be decided as to whether or not the abnormality is clinically significant and the reason for the abnormality will be recorded. The overall evaluation (normal/abnormal) will be reported in ClinBase.

The investigator may add extra 12-lead resting ECG safety assessments if there are any abnormal findings or if the investigator considers it is required for any other safety reason. These assessments should be entered as an unscheduled assessment.

All ECG readings will be digitally stored as source documents.

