#### **12.2.6. Adverse events based on examinations and tests**

The results from protocol mandated safety assessments will be summarized in the CSR.

Deterioration as compared to baseline in protocol mandated safety assessments should therefore only be reported as AEs if they fulfil any of the SAE criteria.

If deterioration in a vital sign or laboratory value is associated with clinical symptoms and signs, the symptom or sign will be reported as an AE and the associated vital sign or laboratory result will be considered as additional information.

Wherever possible the reporting investigator should use the clinical, rather than the laboratory term (e.g., anemia versus low hemoglobin value).

In the absence of clinical symptoms or signs, clinically relevant deteriorations in non-mandated parameters should be reported as AE(s).

Any new or aggravated clinically relevant abnormal medical finding at a physical examination as compared with the baseline assessment will be reported as an AE.

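### The ECG is only listed, although section 12.2.6 relies on mandated safety results being summarized when it keeps non-serious deteriorations out of adverse event reporting

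*Protocol*

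**What the plan says.** **Schedule.** Table 1, footnote 9, places ECGs at screening, at first admission, "1.25 hours after each dose (Visits 2-5, Day 1"), and at follow-up or early termination, for a "total of 7 ECGs per subject who complete the study". Section 5.4.1 states that peak concentrations are "achieved in less than 2 hours".

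**Capture.** Section 9.3.3 has the investigator call each ECG normal or abnormal. For an abnormal ECG, clinical significance is decided and the reason is recorded. The section then states: "The overall evaluation (normal/abnormal) will be reported in ClinBase". Readings are kept digitally as source documents.

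**Analysis.** Section 11.10.3 is one sentence: "12-Lead ECG results will be listed for each subject". The synopsis, under safety data analysis, says: "Other safety data including C-SSRS, physical examinations and ECG will be listed for each subject".

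**Adverse event rule.** Section 12.2.6 begins: "The results from protocol mandated safety assessments will be summarized in the CSR". It concludes from this that a deterioration from baseline in a mandated assessment is reported as an adverse event only if it meets a seriousness criterion.

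**General rule.** Section 11.2 provides for counts and percentages for each qualitative variable. Section 11.1 says that no separate SAP will be written, and allows an abbreviated one for changes to the analyses.

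**The concern.** Section 12.2.6 is a trade. Routine deteriorations need not be reported as adverse events because the reader will find them in the summaries. The trade works for vital signs (section 11.10.2, descriptive statistics by treatment and time-point) and for haematology and chemistry (section 11.10.4, summary and shift tables). The physical examination is only listed, but section 12.2.6 separately makes new clinically relevant examination findings adverse events. The ECG has neither a specified summary nor such a rule.

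At stake is the secondary objective on safety and tolerability. The post-dose ECG is timed near peak for each administration method. If more abnormal ECGs followed one method than the others, the reader would have to find this by going through subject listings.

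**Working it through.** No power or error-rate formula applies. The check is a count and a comparison of passages.

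**1. The plan's own figure.** Screening 1 + first admission 1 + one after each of 4 doses + follow-up 1 = 7 ECGs per completer. This agrees with Table 1, footnote 9. Four of the seven are at 1.25 h.

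**2. Number of near-peak ECGs.** Section 11.4 plans at least 36 evaluable and up to 44 randomized subjects. If between 36 and 44 complete all periods:
- 4 × 36 = 144
- 4 × 44 = 176

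**3. Is another objective assessment scheduled near peak?** From the footnotes to Table 1:

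| Assessment | Times within a treatment period |
|---|---|
| ECG | 1.25 h after dosing (plus Day -1 of period 1 only) |
| Vital signs | admission, then "at pre-dose (0 hours) and post-dose at 24 and 48 hours, as well as at the final follow-up/ET visit" |
| Abbreviated physical examination | admission and 48 h |
| Safety laboratory tests | pre-dose, periods 1 and 3 only |
| Adverse event questioning (subjective) | pre-dose, 3, 12, 24 and 48 h |

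After the ECG, the next objective assessment is vital signs at 24 h. As an illustration, assume a peak at 1.5 h and mono-exponential decline with the half-life of 6 to 11 h given in section 5.4.4. The fraction of peak left at 24 h is 2^(−22.5/t½):
- t½ = 6 h: 2^(−3.75) ≈ 7%
- t½ = 11 h: 2^(−2.05) ≈ 24%

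The 1.25 h ECG is therefore the only scheduled objective safety assessment near peak.

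**4. Where a non-serious, symptom-free ECG deterioration would be reported.**
- Adverse event tables: no, under section 12.2.6, because no seriousness criterion is met.
- ECG summary table: none is specified in section 11.10.3, and the synopsis lists the ECG only.
- Other significant adverse events (section 12.1.3): only if the sponsor's expert judges it of particular clinical importance.
- Subject listing: yes.

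**5. Do the passages agree?** They do not. Sections 12.2.6 and 11.2 imply that the ECG is summarized, whereas section 11.10.3 and the ECG sentence of the synopsis provide only a listing.

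**The case against.** The strongest reply is that the protocol does not rule out an ECG summary. Section 11.2 covers every qualitative variable, and a normal/abnormal call is one. The synopsis says that all safety data are to be summarized as appropriate. Section 12.2.6 promises a summary in the study report, not a table by treatment. This much stands: the document conflicts with itself, and a reader may not infer that the sponsor has settled on no ECG summary. But the ECG-specific sentences are the ones a programmer would follow, and section 11.1 plans no separate SAP to settle the matter.

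There are also other routes into the report. Changes meeting a seriousness criterion are adverse events, accompanying symptoms are collected as adverse events (section 12.2.5), withdrawals are summarized with reasons (section 11.6), and section 12.1.3 provides an expert review. This narrows the gap to non-serious, symptom-free changes that the review does not flag. It does not close it, because a judgement-based review gives no counts by treatment.

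Two stronger readings are tempting and not supported:
- A reader might infer that the ECG is stored only as normal or abnormal. Section 9.3.3 also has clinical significance decided, the reason for an abnormality recorded and the readings stored digitally. The normal/abnormal call is only the result it expressly sends to ClinBase.
- A reader might infer that heart rate and PR, QRS, QT or QTcF values are available and should be analysed. No section mentions obtaining intervals, and storing readings as source documents does not show that exportable values exist. Any estimate of precision for such an analysis would need within-subject standard deviations that the protocol does not give.

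Finally, section 9.1 expects no safety issues, and comparing ECGs between administration methods is not a stated objective. That limits the weight of the point but does not remove the inconsistency.

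**Conclusion.** The point holds as a contradiction between sections. Section 12.2.6 rests an adverse event reporting rule on a summary that section 11.10.3 and the ECG sentence of the synopsis do not provide, and section 11.2 points the other way. It concerns 144 to 176 post-dose ECGs, assuming 36 to 44 subjects complete all four periods. The consequence is confined to non-serious, symptom-free ECG deteriorations not picked up under section 12.1.3. On the ECG-specific text these reach a subject listing but no adverse event table and no by-treatment summary.

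The bioavailability comparisons, their confidence intervals and the sample size are untouched. The count of ECGs and the timing of the assessments come directly from the protocol. Only the 7% to 24% residual exposure rests on assumptions (a 1.5 h peak and mono-exponential decline), and the conclusion does not depend on it.

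**What to change.** In section 11.10.3 and the synopsis, add a table by treatment for the 1.25 h ECG giving n (%) normal, abnormal not clinically significant and abnormal clinically significant. In section 9.3.3, state that the clinical-significance judgement, which the investigator already has to make, is entered in ClinBase with the normal/abnormal call.

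A shift from the Visit 2, Day -1 ECG can be added as an option, with a note on its weakness. Periods 2 to 4 have no pre-dose ECG. With three washouts of at least 7 days, the shift in period 4 would span at least 3 × 7 = 21 days.

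Alternatively, limit the premise of section 12.2.6 to assessments that are actually tabulated, and state which reporting rule then applies to the ECG.

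The table costs one extra output and one data field, with no additional ECG, visit or staff. The alternative is a wording change, but it alters what is recorded as an adverse event, so it should be settled before dosing starts.

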#### **11.10.4. Laboratory assessments**

Hematology and clinical chemistry values will be listed by subject and time-point including changes from baseline and repeat/unscheduled measurements. Summary tabulations will be presented by treatment sequence and time-point for the safety analysis set. The baseline for the measurements will be the pre-dose assessment performed prior to dosing in Treatment period 1. Changes from baseline will be calculated and presented for all post-baseline time-points including pre-dose in Treatment period 3 and the follow up visit. Shift tables will also be presented.

The listings will include the following information: test name, date of measurement, reference range, result and flags for any measurements that are outside the reference range (e.g., AstraZeneca, program, or laboratory ranges). Clinical laboratory data will be reported in the units provided by the clinical laboratory for the Safety Review Committee meeting (if applicable), and in System International units in the CSR.

Additional listings will be presented for the following:

- Urinalysis (macroscopic and microscopic, if applicable)
- Pregnancy testing (including FSH)

**11.10.5. Physical examination and body weight**

The results of the physical examination will be listed by body system for each subject.

Body weight will be listed by subject and time-point.

**11.10.6. Columbia-Suicide Severity Rating Scale**

Results of the C-SSRS will be listed for each subject and time-point.

**11.11. Analysis of exploratory data**

**11.11.1. Taste test assessment**

For Treatment A and C, palatability will be assessed as measured by taste scores. The results of the taste questionnaire will be listed for each subject and treatment, where applicable.

**11.11.2. Pharmacogenetics**

The date and time of the blood sample taken for pharmacogenetics will be listed.

## **12. ADVERSE EVENTS**

### **12.1. Definitions**

#### **12.1.1. Definition of adverse events**

An AE is the development of an undesirable medical condition or the deterioration of a pre-existing medical condition following or during exposure to a pharmaceutical product, whether or not considered causally related to the product.

An undesirable medical condition can be symptoms (e.g., nausea, chest pain), signs (e.g., tachycardia, enlarged liver) or the abnormal results of an investigation (e.g., laboratory findings, ECG).

In clinical studies an AE can include an undesirable medical condition occurring at any time after the subject/patient has signed informed consent, including run-in or washout periods, even if no specific treatment has been administered.

The term AE is used generally to include any AE whether serious or non-serious.

#### **12.1.2. Definitions of serious adverse event**

An SAE is an AE occurring during any study phase (i.e., run-in, treatment, washout, follow-up), that fulfils one or more of the following criteria:

- Results in death
- Is immediately life-threatening
- Requires in-patient hospitalization or prolongation of existing hospitalization
- Results in persistent or significant disability or incapacity or substantial disruption of the ability to conduct normal life functions
- Is a congenital abnormality or birth defect
- Is an important medical event that may jeopardize the subject or may require medical intervention to prevent one of the outcomes listed above

For further guidance on the definition of an SAE, see [Appendix 15.1](#) of this clinical study protocol.

#### **12.1.3. Other significant adverse events**

During the evaluation of the AE data, an AstraZeneca medically qualified expert will review the list of AEs that were not reported as SAEs or AEs leading to withdrawal. Based on the expert's judgment, significant AEs of particular clinical importance may, after consultation

with the Global Safety Physician, be considered as other significant adverse events (OAEs) and reported as such in the CSR. A similar review of other data from vital signs, laboratory assessments and other safety assessments will be performed for identification of OAEs.

Examples of these are marked hematological and other laboratory abnormalities, and certain events that lead to intervention (other than those already classified as serious), dose reduction or significant additional treatment.

## **12.2. Recording of adverse events**

### **12.2.1. Time period for collection of adverse events**

SAEs will be collected from the signing of informed consent and AEs from randomization until the final follow-up visit.

### **12.2.2. Follow-up of unresolved adverse events**

Any AEs that are unresolved at the subject's last visit in the study are followed up by the investigator for as long as medically indicated, but without further recording in ClinBase.

AstraZeneca retains the right to request additional information for any subject with ongoing AE(s)/SAE(s) at the end of the study, if judged necessary.

### **12.2.3. Variables**

The following variables will be collected for each AE:

- AE diagnosis/description
- The date and time when the AE started and stopped
- Intensity
- Whether the AE is serious or not
- Investigator causality rating against the IMP (yes or no)
- AE caused subject's withdrawal from study (yes or no)
- Outcome

Additional variables (e.g., action taken with study drug) will be collected for all SAEs including treatment given for the event.

The following intensity ratings will be used:

1. mild (awareness of sign or symptom, but easily tolerated)
2. moderate (discomfort sufficient to cause interference with normal activities)

3. severe (incapacitating, with inability to perform normal activities)

It is important to distinguish between serious and severe AEs. Severity is a measure of intensity whereas seriousness is defined by the criteria in [Section 12.1.2](#).

An AE of severe intensity need not necessarily be considered serious. For example, nausea that persists for several hours may be considered severe nausea, but not an SAE. On the other hand, a stroke that results in only a limited degree of disability may be considered a mild stroke but would be an SAE.

#### **12.2.4. Causality collection**

The investigator will assess causal relationship between IMP and each AE, and answer “yes” or “no” to the question: *“Do you consider that there is a reasonable possibility that the event may have been caused by the investigational product?”*

For SAEs causal relationship will also be assessed for study procedures. Note that for SAEs that could be associated with any study procedure the causal relationship is implied as “yes”.

A guide to the interpretation of the causality question is found in [Appendix 15.1](#) of this clinical study protocol.

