### **8.6. Doses and treatment regimen**

Each subject will receive single dose treatments of naloxegol on four occasions in the fasted state. AstraZeneca will provide detailed dispensing and handling instructions for each product and treatment, including the amount of water to be taken with each treatment.

- **Treatment A:** Naloxegol 25 mg (1 tablet) crushed, suspended in water, given orally
- **Treatment B:** Naloxegol 25 mg (1 tablet) crushed, suspended in water, given via nasogastric tube (total of 200 mL water)
- **Treatment C:** Naloxegol 25 mg (10 mL oral solution)

- **Treatment D:** Naloxegol 25 mg (1 tablet) whole tablet, given orally

Non-carbonated water, 240 mL, at room temperature will be used, as applicable. Use of mineral water for dosing is not allowed.

Subjects will be required to be fasted for at least 10 hours before dosing.

Food and water restrictions, as well as posture control are described in [Section 7.5](#).

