- If the start day and month are missing the date will be imputed as the first day of dosing in the known year unless the end date is known and shows that the AE ended before a dose was given in that year; in which case the start day and month will be imputed as 01Jan or with the date of Screening if this is later. If the end date is non-informative (i.e., is missing or does not contain enough information), the start date will be imputed as the first date of dosing in the known year. If the year is not a year of dosing then the date will be imputed as 01Jan or with the date of Screening if this is later.
- Missing times will be imputed as 00:00 h or with the time of dosing for events starting on a dosing day.

Adverse events will be summarized by treatment (where treatments will be pooled across the treatment periods) and overall, including tabulations by causality and severity (mild, moderate and severe). All tabulations will be presented by SOC and PT. Furthermore, listings of SAEs and AEs that led to withdrawal will be made and the number of subjects who

had any AEs, SAEs and AEs that led to discontinuation will be summarized. The AEs that occur before (first) dosing will be excluded from the summary tables.

The following information will be included in the listings: verbatim term, MedDRA SOC, PT and lowest level term, start date/time, end date/time, time from last dose, causality, action taken, whether the AE was classified as serious and the outcome.

All tabulations will include the number and percentage of subjects.

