### **12.3. Reporting of serious adverse events**

All SAEs have to be reported, whether or not considered causally related to the IMP, or to the study procedure(s). All SAEs will be recorded in ClinBase.

If any SAE occurs in the course of the study, then investigators or other clinical unit personnel will inform appropriate AstraZeneca representatives immediately, or **no later than 24 hours** of when he or she becomes aware of it.

The designated AstraZeneca representative will work with the investigator to ensure that all the necessary information is provided to the AstraZeneca Patient Safety Data Entry Site **within 1 calendar day** of initial receipt for fatal and life-threatening events and **within 5 calendar days** of initial receipt for all other SAEs.

For fatal or life-threatening AEs where important or relevant information is missing, active follow-up will be undertaken immediately.

Investigators or other clinical unit personnel will inform AstraZeneca representatives of any follow-up information on a previously reported SAE immediately, or **no later than 24 hours** of when he or she becomes aware of it.

In addition to recording of SAEs in ClinBase, the AstraZeneca Serious Adverse Event Report – Clinical Study form for reporting an SAE to the Data Entry Site (DES) will also be used.

All information provided for the SAE sent into the DES will be in English.

The following CRF modules will be completed for each SAE report:

- Demography
- Dosing
- AE (including start and stop date/time for the AE, the investigator's causality assessment to study drug, action taken with study drug, severity and outcome)

- 
- SAE (including serious criteria, causality assessment to study procedure any investigations, the symptoms and course of the event and any treatments given)
  - Medical History
  - Concomitant Medications
  - LIVERRF (risk factors), LIVERSS (signs and symptoms) and LIVERDI (additional diagnostic with results) for all SAEs with a reported term of ‘potential Hy’s Law’ or ‘Hy’s Law’ will be provided in a narrative form by the PI
  - Any additional supporting information e.g., laboratory test results, vital signs, ECG assessments

The ‘AstraZeneca first aware date’ for all SAEs reported is the date that any member of the Provider or AstraZeneca first become aware of the SAE and for regulatory reporting purposes this is the ‘clock start date’.

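### Causality to study procedures is collected only for serious events, so the safety tables do not identify non-serious nasogastric-tube events in Treatment B as a category

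*Protocol*

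**What the plan says.** Section 8.6 gives Treatment B as a tablet "crushed, suspended in water, given via nasogastric tube (total of 200 mL water". Treatment A is the same crushed tablet taken by mouth: "Naloxegol 25 mg (1 tablet) crushed, suspended in water, given orally". Treatments C (oral solution) and D (whole tablet) involve no tube.

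On causality, section 12.2.4 states that "The investigator will assess causal relationship between IMP and each AE", and the variable listed in section 12.2.3 is "Investigator causality rating against the IMP (yes or no". Procedure causality is added for serious events only: "For SAEs causal relationship will also be assessed for study procedures". In section 12.3 it accordingly appears in the serious-event module: "SAE (including serious criteria, causality assessment to study procedure any investigations".

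On reporting, section 11.10.1 summarizes adverse events by treatment, pooled over periods, and overall, "including tabulations by causality and severity (mild, moderate and severe". It adds that "All tabulations will be presented by SOC and PT".

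**The concern.** One arm of this crossover carries an invasive procedure that the other three do not. The natural tube complaints (discomfort, gagging, nosebleed, retching) will rarely be serious, so the procedure question will rarely be asked about them. The only causality variable for such an event is the drug rating, and that rating feeds the causality table by treatment.

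At stake is how the Treatment B column is read. The secondary objective in section 6.2 is the safety and tolerability of single doses of naloxegol. To serve it, a reader needs to know how far any pattern under B reflects the drug and how far it reflects the tube. A later analysis plan could not repair the gap, because a field that was never collected cannot be tabulated. Section 11.1 in any case says that no separate plan will be written.

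**Working it through.** The protocol has no figure to reproduce here. The check sets its sections side by side.

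**1. What is collected.** Sections 12.2.3 and 12.2.4 give one causality item for every adverse event: investigational product, yes or no. Sections 12.2.4 and 12.3 give a second item, study procedure, for serious events only. The two sets of text agree with each other. For a non-serious event the second item does not exist.

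**2. Where a non-serious event goes.** Its true cause may be drug, tube, both or neither. The recorded item has two levels.

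- Clear tube cause: Appendix 15.1 makes the absence of an alternative cause one of its factors, and finds no reasonable possibility where another cause is more likely. The event can be rated no. It then shares that level with every background event.
- Tube or drug both plausible (for example nausea or retching soon after dosing): Appendix 15.1 tells the investigator to treat ambiguous cases as a reasonable possibility. The event is rated yes.

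So tube and neither share one level, while drug, both and ambiguous share the other. Neither level identifies the tube, and the tube can add ambiguous events only in Treatment B.

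**3. Which treatment column the event enters.** Section 8.8 sets the Treatment B dosing time as the moment the product is fully administered into the tube, so insertion comes before dosing. Section 11.10.1 assigns an event that starts before dosing in one period to the preceding period. Events before the first dose are kept out of the summary tables. For an event that starts after insertion but before the dosing time:

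| Sequence | Period of B | Where the event is counted |
|---|---|---|
| ADBC | 3 | Treatment D |
| BACD | 1 | left out of the summaries |
| CBDA | 2 | Treatment C |
| DCAB | 4 | Treatment A |

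Section 11.4 plans 9 subjects per sequence for 36 evaluable subjects. If 44 were spread equally, there would be 44 / 4 = 11 per sequence. Three of the four sequences place such an event under another treatment: 3 × 9 = 27 of 36 insertions, or 3 × 11 = 33 of 44. The fourth leaves it out: 9 of 36, or 11 of 44. None of these events is counted under B.

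This applies only to events with a recorded onset before dosing. Events starting at or after the dosing time fall under B as intended. So does an event with a missing start time on the dosing day, if the time of dosing is imputed. The protocol does not say how long before dosing the tube is placed; handling instructions are separate.

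**The case against.** The strongest reply is that the scheme is coherent and loses little. Rating the drug for all events and the procedure for serious ones is applied consistently. A nosebleed on insertion can properly be rated unrelated to naloxegol. The tables go down to preferred term, and the listings show verbatim term, start date and time, and time from last dose, so a clear tube event stays visible. Treatment A gives the same crushed tablet by mouth to the same subjects, so B against A offers an indirect contrast for the tube. A procedure field would rest on the same investigator's judgement, and many ambiguous events would end up in both.

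Most of this stands. A reader might infer that tube events can only be charged to the drug, or that the data cannot separate tube from naloxegol at all. The documents do not support that: the drug item separates the causes whenever the investigator can tell them apart, and the listings and the A contrast help further.

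Three things remain. Clear tube events have no category of their own. Ambiguous ones lean towards drug-related by the protocol's own rule. The B against A contrast attributes no individual event, and the allocation rule can place insertion events from sequence DCAB in the A column itself.

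**Conclusion.** The point holds in a limited form. Non-serious tube-related events are not identified as a category in the by-treatment causality tables, and events that could come from either cause default to drug-related. This touches only the secondary safety objective, which is descriptive with no inferential comparison of event rates planned. The primary pharmacokinetic analysis is unaffected. It is a cheap improvement that must be made before data collection, not a flaw that endangers the trial.

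Two further inferences should not be drawn. First, that tube events are expected: section 7.6.1 only requires subjects to say that they are willing and able to tolerate the tube, and no section predicts such events. Second, that a particular number of events is at stake. If 10% to 50% of insertions caused a non-serious event, 36 × 0.10 = 3.6 to 44 × 0.50 = 22 events would follow. That range is an assumption multiplied out, and the protocol supplies no rate. Nor does it supply a base rate to support a claim that one or two misrated events would reverse a comparison of B with D. The allocation result depends on the section 8.8 dosing time and on the onset being recorded as before dosing.

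**What to change.** In sections 12.2.3 and 12.2.4, extend the procedure-causality item already used for serious events (yes or no) to every adverse event. In section 11.10.1, tabulate events by treatment as drug-related, procedure-related, both or neither.

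In the same table, assign events that start at or after tube insertion but before the Treatment B dosing time to Treatment B, including those in sequence BACD that would otherwise drop out. Without this rule the new procedure column would show some tube events under the wrong treatment. It requires the insertion time to be recorded, if the handling instructions do not already ask for it.

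The cost is one more CRF field per event and a somewhat larger table. The new item still relies on investigator judgement, and some events will remain in both.
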